5.2 Eligibility

All participants invited to this study are considered eligible.

- 5.3 Recruitment
Information to be included in the CONSORT flow diagram.
- 5.4 Withdrawal/follow-up
The level of reported oil consumption per time unit and overall will be presented. The number of participants with last reported data will be presented for each data collection time-point.
- 5.5 Baseline patient characteristics
The following baseline variables² will be presented for each treatment group and overall:

- Age group
- Gender
- Weight
- Height
- BMI
- Occupational status
- Education level
- Household income
- Household count
- Children living at home
- Smoking habits
- Chronic disease (Yes/No)
- Parents ethnic origin
- Skin type
- Sun exposure (July to October 2020)
- Dietary intake:
 - Vitamin D supplement
 - Omega-3 supplement
 - Cod liver oil
 - Fatty fish intake

Follow-up variables:

- Compliance
- Airways infections
- SARS-CoV-2-tested (negative and positive)
- Dyspnoea (among COVID positive participants)
- Side effects (counts (%)), self-reported free-text fields

Lab

- Vitamin D (baseline and change from baseline)
- Omega-3 index (baseline and change from baseline)
- Baseline serology

MSIS data:

- Positive and negative test results

² The specific SAS variable names in the received data set are presented in Appendix 1.

For continuous baseline variables N, mean, standard deviation, median, minima and maxima will be presented. For categorical variables, N and Per cent will be presented for each oil group.

6. Analysis

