6.4 Harms

Adverse events will be presented for each treatment group, at each reporting time and accumulated over the whole study duration from start of oil consumption.

Data will be summarized in tables of means and medians for continuous variables and tables of counts for discrete variables. Sufficient detail on summarizing safety data, e.g., information on severity, expectedness, and causality; details of how adverse events are coded or categorized; how adverse event data will be analysed, i.e., grade 3/4 only, incidence case analysis, intervention emergent analysis

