cancer	difference in lung cancer incidence in	of vitamin D in cod
	postmenopausal women (RR 0.90, 95% CI 0.39 to	liver oil lung cancer
	2.08; 3 RCTs, 37601 women; low-certainty evidence).	indidence?

Benefit/Risk Assessment

Based on existing literature and data from Koronastudien, we have identified cod liver oil as a supplement that may prevent Covid-19 and or reduce the severity of the disease and found that the benefit of testing this in a randomized study far outweighs the risks. A full benefit/risk assessment is found in the Ethics section.

3. Objectives and endpoints

Based on the encouraging results from Koronastudien as well as existing evidence from the literature, we aim to investigate whether cod liver oil can prevent Covid-19, serious Covid-19, or other respiratory tract infections.

We also aim to explore and confirm already known health effects and possible new health effects, in particular rare adverse events associated with cod liver oil use. This will be done during a follow-up period of up to two years after the end of the cod liver oil period

We hypothesize that:

Intake of cod liver oil can prevent Covid-19 disease Intake of cod liver oil can prevent serious Covid-19 Intake of cod liver oil can prevent other airway infections

These hypotheses will be tested in a triple-blinded randomized placebo-controlled study where 80.000 participants will be assigned to cod liver oil or placebo in a 1:1 ratio.

The safety of cod liver oil will be explored.

Finally, it is a separate aim of the study to identify the mechanisms of action of any health effects seen.

Definition of endpoints

A. Number of participants diagnosed with serious Covid-19 (primary endpoint)

The number of participants with first time SARS-CoV-2 positive nasopharyngeal and or pharyngeal swabs (or any other sample used for detection of current disease) analyzed by reverse transcriptase quantitative polymerase chain reaction (RT-qPCR) nucleic acid amplification test or antigen tests [18] used by accredited Norwegian microbiology laboratories in the period from one week after the start of cod liver oil/placebo taking to the end of the study period together with any of the following:

A) Self-reported dyspnea concurrent with the positive test

OR

B) self-reported hospitalization caused by Covid-19 concurrent with the positive test OR

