*Influenza virus (A and B), parainfluenzavirus (1,2,3), metapneumovirus, rhinovirus, coronavirus (non-SARS), Respiratory Syncytial virus, Haemophilus Influenzae, Moraxella Catharralis, Streptococcus Pneumonia, Beta-hemolytic streptococci, Mycoplasma pneumonia, Chlamydophila pneumonia, Enterovirus, Bordetella pertussis. The list can be expanded based on the analyses performed in Norwegian Microbiology laboratories.

Exploratory during follow up of up to two years

- Cardiovascular disease incidence and mortality during the study period or follow up
- Cancer incidence and mortality during the study period or follow up
- All-cause mortality during the study period or follow up
- Fracture of the hip or forearm during the study period or follow up
- Incident dementia during the study period of follow up

Endpoints at six months:

All primary endpoints tested in the final statistical analysis plan will be tested six months after unblinding (the end of the cod liver oil or placebo taking period).

Safety

The safety of the intervention will be followed for two years after the end of the cod liver oil taking period. This will be done by observing all-cause mortality and hospital admissions for major disease groups in the cod liver oil versus the placebo group in Norwegian registries.

4. Study Design

Overall Design

The CLOC study will include 80.000 participants that will be randomized in a 1:1 ratio to consume 5 ml cod liver oil or placebo (corn oil) with lemon taste per day for 6-12 months.

The study will be organized as a ancillary study of "Koronastudien", a cohort study investigating Covid-19. Participants will be a subgroup of participants in Koronastudien, and relevant data from these participants will be shared among the studies.

Koronastudien has collected extensive electronic questionnaire data using the University of Oslo webbased solution "Nettskjema". Koronastudien aims to identify risk factors associated with the community- and workplace acquisition of Covid-19 virus and also aims to identify risk factors for the progression of the disease and to understand the virus and disease themselves.

Scientific Rationale for Study Design

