All blood- and other biological samples collected as part of the study will be stored in this biobank.

Questionnaires and consent forms

Participants will already have completed the Koronastudien questionnaires containing questions about risk factors for Covid-19, supplement use, travel history, cancer, cardiovascular disease, and other previous diseases, skin-type, sunlight exposure, and demographic variables). During the study period, it is expected that 1-2 Koronastudien specific follow-up questionnaires will be distributed, and these will be coordinated to reduce the burden of participation. In addition, the following data will be collected from the sub-study participants using electronic forms:

- Screening questionnaire before inclusion (inclusion and exclusion criteria)
- Consent form. The identity of each participant in Koronastudien is known through the consenting procedure using two-factor authentication with Bank ID. The consent form for Transtudien will be sent as a unique link to existing participants, and consenting will be a simple yes or no checkbox at the end of the form without requiring further identification with Bank ID.
- Baseline questionnaire: Diet including an estimate of vitamin D and n-3 LCPUFA intake and other baseline data collection will be coordinated with a follow-up questionnaire in Koronastudien to reduce participant burden.
- Every month: Compliance, use of supplements, side effects, efficacy of blinding, endpoints
- End of study: FFQ (a validated web-based food frequency questionnaire), risk factors for Covid-19 and other relevant diseases, use of supplements, previous conditions, side effects, efficacy of blinding, endpoints
- Follow-up up to two years: Diet, use of supplements, endpoints.

Participants will also be encouraged to report any symptoms of respiratory tract infections and any possible side-effect during the cod liver oil taking period using an electronic questionnaire available to them at all times during the study period.

Dietary questions on vitamin D and n-3 LCPUFA will be based on the FFQ.

Registries

Data for validation of endpoints, previous diseases, and risk factors will be obtained from the following registries (registry, data to be obtained):

- Causes of death: death, and cause of death
- Hospital records: verification of endpoints
- KUHR: visits to GP and cause of visit
- Norwegian Prescription database:, medications

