- MSIS (the Mandatory Norwegian Surveillance System for Communicable Diseases): Covid-19 status,- negative and positive SARS-CoV-2 tests.
- The Norwegian Patient Registry (NPR): Hospital admissions and outpatient visits: fractures, health-related events and endpoints
- The patients' general practitioner or treating physician may be contacted for verification of endpoints, adverse effects, and causes of death

- Luftveisdatabasen (Airway Database), Covid-19 status, other PCR and culture verified infections
- Microbiology laboratories, microbial test results not available through Airway Database (HelseNorge.no)
- Other statutory health registries including the Norwegian Pandemic Registry and heart registry
- Folkeregisteret and The Contact and Reservation Registry, contact information, address
- Quality Registries on Covid in Oslo University Hospital, detailed data about risk factors for Covid-19 and outcome of disease

Assessment of dietary and Supplemental Intake Questionnaire

Simple questions about the intake of vitamin D and n-3 LCPUFAs (based on a validated, selfadministered semi-quantitative food frequency questionnaire (FFQ)) will be distributed to participants at baseline. Classifying participants by baseline intake of various nutrients will allow us to evaluate whether the study agents' effects vary by such intake. Participants will be asked to complete a complete FFQ.

Questions on the use of non-study supplements or drugs containing vitamin D or EPA+DHA will be asked at baseline and end of the study and on follow-up questionnaires. We will ascertain and analyze intake from food and supplements separately, and from both sources combined.

Follow up

At the end of the intervention, three, six months, 12 and 24 months later, a questionnaire will be sent to participants. The form will be similar to the conventional follow-up questionnaires, collecting information about potential risk factors, major diseases use of medications, and medical history. The additional data will be used to address the duration of any effects seen on the primary endpoints and any side effects of the intervention as well as to explore other health effects of cod liver oil as described in the endpoint section.

Data management

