The study aims to identify the health effects of cod liver oil as a supplement to the normal diet of participants not normally using such supplements. Most people have a relatively stable diet over many years, and the study will attempt not to interfere with the diet of participants. We consider that continuing to have the same diet as before during a study period that lasts less than one year poses a negligible risk to participants.

However, the Norwegian dietary recommendations for vitamin D are complicated and depend on how much fish you eat, your age, the season, and your sun exposure. Based on the collected data, participants at high risk for vitamin D or low levels of n2-LCPUFFA will be notified at the end of the study and recommended to discuss their diet with their general practitioner and or get their vitamin D levels and 3n-LCPUFA levels measured.

No measurements of vitamin D or 3n-LCPUFA will be made before unblinding, and this will not be known to the study during the cod liver oil/placebo taking period.

Expected side-effects

Several side-effects have been described for intake of fish oil and low-dose vitamin D, but in practice, very few serious side effects are expected to be found.

For fish oil the following side effects have been described: gastrointestinal (GI) symptoms (stomach upset or pain, nausea, constipation, diarrhea), bleeding (any GI bleed, GI bleeding requiring transfusion, hematuria, easy bruising, epistaxis), skin rash, colds or upper respiratory tract infection, flu-like symptoms, bad taste in the mouth

For vitamin D, the following side effects have been described: GI symptoms as listed above, and hypercalcemia or kidney stones.

Each follow-up questionnaire will contain questions about side-effects.

Importance of study results and generalizability

There is a significant inherent risk in the study that the Covid-19 prevalence becomes much lower than the threshold for detection of any effect or that a Covid-19 cure or vaccine becomes available, making the study results less relevant. However, the primary endpoints of respiratory tract infections will still be of great importance; likewise, the in-depth safety characterization of cod liver oil will be of importance.

Benefits

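### None of the harms the protocol names (kidney stones, hypercalcaemia, bleeding) is a pre-specified registry safety outcome, and outpatient or GP-managed cases fall outside the registry safety comparison

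*Combined protocol and SAP*

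**What the plan says.** Section 3 of the protocol sets an aim of exploring known and new health effects, "in particular rare adverse events associated with cod liver oil use". Under Safety, the same section gives the method: "The safety of the intervention will be followed for two years after the end of the cod liver oil taking period", by "observing all-cause mortality and hospital admissions for major disease groups in the cod liver oil versus the placebo group" in Norwegian registries. Neither document lists or defines the major disease groups.

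Protocol section 10 (Expected side-effects) names what has been described for each constituent. For fish oil it lists gastrointestinal symptoms and bleeding (including GI bleed, haematuria and epistaxis). For vitamin D it lists "GI symptoms as listed above, and hypercalcemia or kidney stones".

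Protocol section 8 (Registries) says what will be obtained. From the Norwegian Patient Registry (NPR) this is "Hospital admissions and outpatient visits: fractures, health-related events and endpoints". For general practice it is "KUHR: visits to GP and cause of visit". Under Endpoint Ascertainment, section 8 adds that NPR receives diagnoses for both inpatients and outpatient visits.

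The SAP lists, among the follow-up variables in 5.5, "Side effects (counts (%)), self-reported free-text fields". SAP 6.4 presents adverse events by arm, at each reporting time and cumulatively: "Data will be summarized in tables of means and medians for continuous variables and tables of counts for discrete variables". The sentence that follows in 6.4 lists what a harms section should contain (severity, coding, type of analysis) without supplying it.

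**The concern.** The outcome scale in the safety rule does not match the harms the protocol expects. A stone or a bleed can count only if it leads to admission, and then only as part of a group whose breadth is unknown. A case handled in an outpatient clinic or by a GP does not enter the comparison, although the trial plans to hold data on such contacts.

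The stake is the safety aim, not efficacy. Section 10 says the in-depth safety characterisation will be important even if COVID-19 incidence is low. A null comparison of broad admission groups would say little about the harms the protocol itself lists.

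**Working it through.** **Step 1: compare the texts.** The plan states no figure on this point, so the main check is whether any planned outcome isolates a named harm.

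| Where | Planned outcome | Isolates stones, hypercalcaemia or bleeding? |
|---|---|---|
| Protocol 3, primary | Four COVID-19, test and airway-infection endpoints | No |
| Protocol 3, secondary | COVID-19 hospitalisation and ICU care, any admission, infections, GP visits | No; admissions and GP visits are not cause-specific for these harms |
| Protocol 3, exploratory | Cardiovascular disease, cancer, mortality, hip or forearm fracture, dementia | No |
| Protocol 3, Safety | All-cause mortality, admissions by major disease group | None specified; groups undefined; admissions only |
| SAP 5.5 and 6.4 | Self-reported side effects, tabulated by arm | No category or coding rule; no between-arm estimate |

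So no planned outcome isolates a named harm. The safety rule uses only the admission part of the NPR data and none of the GP data.

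**Step 2: illustrate what grouping can cost.** The 40,000 per arm comes from the target of 80,000 randomised 1:1 (SAP 3.1). Every incidence below is an assumption, because the documents give none.

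Wald test on the log risk ratio, two-sided 5%:

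- SE = √[(1−p0)/(n·p0) + (1−p1)/(n·p1)]
- z = ln(p1/p0)/SE
- power ≈ Φ(z − 1.96)

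Take a harm with a 0.1% placebo risk that doubles to 0.2%, an excess of 0.1 percentage point. In the group rows, the same excess is added to a group that is otherwise unaffected, and every case is assumed to be admitted.

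| Outcome analysed | Expected participants with event, placebo vs oil | RR | SE | z | Power |
|---|---|---|---|---|---|
| Specific harm | 40 vs 80 | 2.00 | 0.1935 | 3.58 | 95% |
| 0.5% group | 200 vs 240 | 1.20 | 0.0955 | 1.91 | 48% |
| 1% group | 400 vs 440 | 1.10 | 0.0687 | 1.39 | 28% |
| 2% group | 800 vs 840 | 1.05 | 0.0489 | 1.00 | 17% |
| 3% group | 1,200 vs 1,240 | 1.033 | 0.0399 | 0.82 | 13% |

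Worked line for the specific harm: SE = √(0.999/40 + 0.998/80) = 0.1935; z = 0.6931/0.1935 = 3.58; Φ(1.62) ≈ 0.95.

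Other assumed rates show the same pattern. For 0.05% to 0.1%, power is 72% alone and 7% in a 2% group. For 0.2% to 0.3%, it is 80% alone and 17% in a 2% group.

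**Step 3: smaller excesses on the specific outcome (placebo risk 0.1%).**

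- RR 1.5 (40 vs 60): SE 0.2040, z 1.99, power 51%.
- RR 1.3 (40 vs 52): SE 0.2102, z 1.25, power 24%.

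For RR 1.3 the expected 95% CI is 1.3 × exp(±1.96 × 0.2102), or 0.86 to 1.96. A specific outcome therefore gives a usable interval for the named harm but does not assure detection.

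**The case against.** A reader might infer that the plan lumps these harms away or misses them altogether. The documents do not support that reading, for two reasons.

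- Major disease groups is an undefined term. Broad groups are the natural reading, but a narrow renal or bleeding group is not excluded. The dilution figures depend on an assumed group size: power for the doubling is 48% in a 0.5% group and 13% in a 3% group.
- The harms can be captured elsewhere. Side effects are asked about monthly and can be reported at any time on an open electronic form (protocol section 8). Questionnaires at the end of the intervention and 3, 6, 12 and 24 months later also address them, and treating physicians may be contacted to verify adverse effects. GP visits and any admission are secondary endpoints, though not cause-specific for these harms.

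Other objections carry weight:

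- SAP 3.6 covers the four primary variables and sends secondary variables to another SAP, so registry safety may simply come later. Neither document promises a later safety SAP, however, and SAP 6.4 is where harms are placed.
- The safety follow-up is worded as beginning when intake ends. If only that period counts, the illustration requires the excess to persist after intake stops. Any fix must therefore state its window.
- Section 8 gives the purpose of the registry data as validating endpoints, previous diseases and risk factors. It is not established that the extracts cover every relevant diagnosis.
- The protocol expects very few serious side effects and relies partly on exclusions. Section 10 lists a history of kidney stones among these, but the exclusion criteria in section 5 do not; the two passages must be reconciled.

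What remains is that no named harm is a pre-specified registry outcome, that non-admitted cases are outside the registry safety comparison, and that the self-report route has no coding rule or planned estimate.

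**Conclusion.** The point holds as a gap in outcome specification. The registry safety comparison is limited to mortality and admissions for undefined groups, although the trial names specific harms, aims at rare adverse events, and plans to obtain outpatient and GP data that bear on them. It does not hold as a claim that the harms go unrecorded or that broad grouping is a stated rule.

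The size is illustrative only. It rests on 40,000 per arm, which is a target, on assumed incidences, on every case being admitted in the grouped rows, and on the excess falling inside the counted window. The gain from specific outcomes is an interpretable estimate and confidence interval for each named harm; for risk ratios of 1.3 to 1.5, power stays at about 24% to 51%. No primary test, alpha allocation or efficacy estimate is affected. This is a worthwhile low-cost improvement to the safety analysis.

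**What to change.** Amend protocol section 3 (Safety) and SAP 6.4 as follows.

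1. Keep the mortality and disease-group admission comparisons, and define the major disease groups before unblinding.
2. Add kidney stones, hypercalcaemia and bleeding (GI bleed, haematuria, epistaxis) as registry safety outcomes. Count participants with at least one such diagnosis in NPR (admission or outpatient) or KUHR, within the extracts the trial obtains.
3. State the window: from start of intake through the end of safety follow-up.
4. Report participants with an event by arm and the risk ratio with 95% CI, labelled as safety and outside the fallback alpha.
5. Replace the unfilled wording in SAP 6.4 with a coding rule: free-text side effects coded, blind to arm, to the categories in protocol section 10.

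The cost is amended wording, a short diagnosis-code list and some blinded coding. It requires no extra visits or participants. If an extract turns out not to cover one of these diagnoses, that limit should be reported. The downside is a few more safety comparisons without multiplicity control, which the labelling should make plain.
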